
 
To assess the functional non-neutralizing Fc-effector antibody responses prior to (Day 1) and following receipt of 2018/2019 Fluzone and Flublok with and without AF03 or Advax-CpG55.2 adjuvant.
 
	
 
GMT of functional non-neutralizing Fc-effector antibodies against vaccine strain antigens at baseline (Day 1) and approximately Day 29 after vaccination for each study group.
 
Geometric mean fold rise (GMFR) in functional non-neutralizing Fc-effector antibody titers from baseline (Day 1) against the 2018/2019 QIV strains at approximately Day 29 for each study group
 

 
To assess responses from baseline (Day 1) in transcriptomic profiling on approximately Days 2 and 8 following receipt of 2018/2019 Fluzone and Flublok with and without AF03 or Advax-CpG55.2 adjuvant.
 
	
 
Differential expression of transcription profiles comparing samples taken just prior to (Day 1) and on approximately Days 2 and 8 following receipt of the 2018/2019 QIV vaccination in at least a subset of subjects for each study group .
 

 
To evaluate the relationship of non-neutralizing Fc-effector antibodies titers with HAI and NA responses following receipt of 2018/2019 Fluzone and Flublok with and without AF03 or Advax-CpG55.2 adjuvant.
 
	
 
The association of non-neutralizing Fc-effector antibodies GMT with HAI and Neut antibody GMT, seroprotection and seroconversion rates to variant influenza strains and the 2018/2019 QIV vaccine strains.
 

 
To describe the non-neutralizing Ab responses to different influenza HA antigens by a multiplex ELISA assay at all time points in each study group
 
	
 
Quantification of HA binding antibodies against different influenza HA antigens at baseline (Day 1) and Days 8, 29, 57, 90, 118, 180 and 365 in each study group.
 

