## **11 STATISTICAL CONSIDERATIONS**

### **11.1 Introduction**

The goal of this clinical study is to assess, in healthy adults ages 18-45, the safety, reactogenicity and immunogenicity of either the 2018/2019 seasonal Fluzone or Flublok QIV manufactured by Sanofi Pasteur administered intramuscularly given without adjuvant or with one of two adjuvants, AF03 or Advax-CpG55.2. These study arms are included to allow evaluation of the potential of each of the two adjuvants to enhance the immune response to either the 2018/2019 seasonal Fluzone QIV or the 2018/2019 seasonal Flublok QIV.

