### 11.4.2 Subject Enrollment and Follow-up

Based on the accrual rates observed in similar studies, it seems reasonable to expect that the participating VTEUs will be able to enroll this trial in a timely fashion. In a previous DMID trial (DMID 15-0064, NCT02624219), 4 VTEUs recruited 275 healthy subjects, 19 to 64 years of age, in 20 weeks. In this trial, approximately 3% of subjects, 19 to 64 years of age, were excluded from the per protocol (PP) analysis for the Day 22 primary immunogenicity outcome either because they were lost-to-follow-up or because they had a protocol deviation requiring their exclusion from the PP analysis. The rate of per protocol exclusions for the Day 29 visit in this protocol is expected to follow a similar trend.

A total of 40 subjects will be enrolled and randomized in each group. Assuming up to 3% drop out by Day 29, it is expected that at least 38 subjects per group will be available for the primary immunogenicity analysis. If Advax-CpG55.2 is not available, the study will proceed only with groups 1, 2, 4 and 5 open for enrollment for the remaining subjects (up to 240 or 60 per group) in groups 1, 2, 4 and 5. In this case, assuming the same dropout rate of 3%, it is expected that at least 58 subjects per group will be available for the primary immunogenicity analysis.

Follow-up will consist of 2 segments. The first encompasses the core data for this trial and will consist of results for all study visits through approximately 28 days after study vaccination. The second segment consists of a 6-month immunogenicity assessment and follow-up safety assessments through approximately 12 months after study vaccination.

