4.4.3. Method of Assigning Subjects to Study Arms (Randomization)

Enrollment/randomization will be performed through the enrollment module in the electronic data capture system maintained by the Statistical and Data Coordinating Center (SDCC).

Eligible subjects will be stratified by clinical site and prior receipt of licensed, seasonal influenza vaccine (defined as receipt of at least one of the 2017/2018 and/or 2018/2019 influenza vaccines) and randomly assigned with allocation (1:1:1:1:1:1) to one of 6 study arms indicated in [Table 1](#). The treatment sequence was generated using permuted block randomization to provide an approximately balanced allocation to the study arms during the study.

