5. SAMPLE SIZE CONSIDERATIONS

This study is planned to enroll a total of 40 subjects in each group. This study is not designed to test a formal null hypothesis. Rather, it is intended to obtain sufficient data to obtain meaningful estimates of the immune response and to uncover any safety issues that occur at a sufficiently high rate that they might be observed in a study of this size. As such, the type one error rate, $\alpha = 0.05$, is not adjusted for multiple comparisons. While this study is not designed to test any specific null hypothesis, the following tables illustrate the precision and power that is available for select estimates and comparisons of interest.

[Table 3](#) indicates the probability of observing one or more safety events, such as solicited injection site or systemic reactogenicity events or an unsolicited non-serious AE of a particular type for sentinel subjects (N=4 or 6), for a single adjuvanted/ unadjuvanted study arm/stratum (N = 40 or 60), for all subjects receiving the same seasonal QIV (N= 120), for all subjects in the trial (N=240).

Binomial confidence intervals (CI) are widest (have the least precision) when the response rate is 50%.

[Table 4](#) is presented to indicate the worst-case scenario for precision of observed exact (Clopper-Pearson) binomial confidence intervals.

[Table 5](#) illustrates the minimum detectable differences in the proportion of subjects responding (e.g., attaining seroconversion or a titer $\geq 1:40$) between two adjuvanted study arms using a two-sided Likelihood Ratio Test and $\alpha = 0.05$.

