[Implementation Note: A generic sample figure is shown below. Planned Study Day (1,8,29, 57,90,118, 180,365) is plotted along the x-axis, with visit labels as tick labels. Titer is plotted on the y-axis on the log-10 scale. GMT should be plotted at each visit for each strain. Different attributes such as line color, marker shape, line style, line transparency will be used to distinguish strains within a similar grouping. Groupings provided by Sanofi will be used. Six panels will be created to represent the different study arms.]

[figure not shown]

Figure 89: Geometric Mean Titers of NA Binding Antibodies Against Different Influenza NA Antigens by Study Day and Study Arm, Per Protocol Population

[Implementation Note: A generic sample figure is shown below. Planned Study Day (1,8,29,57,90,118, 180,365) is plotted along the x-axis, with visit labels as tick labels. Geometric Mean titer is plotted on the y-axis. GMT should be plotted at each visit for each of the 9 strains with different marker shapes/colors for each strain. Each strain should have a separate color and marker shape. Three panels will be created with each panel representing study arms 1,2, or 3]

[figure not shown]

Figure 90: Association of Non-Neutralizing Fc-effector Antibody Titers and Hemagglutination Inhibition Antibody Titers against 2018/2019 QIV Strains by Study Day and Study Arm, Per Protocol Population

[Implementation Note: A generic scatter plot is shown below. HAI antibody titers are plotted along the x-axis (x-axis label: HAI Titer) and Fc-effector antibody Titers are plotted on the y-axis (y-axis label: Fc-effector Titer). Each study arm will be represented as follow: The same color will be used for the same vaccine (Flublok vs. Fluzone), the same symbol (circle, triangle, square) will be used to indicate the name adjuvant (i.e. no adjuvant, AF03, Advax), and filled vs. unfilled will be used to distinguish adjuvanted vs. unadjuvanted groups.. The spearman correlation should be calculated over all subjects and annotated within each panel as “Spearman Correlation (r=0.xx, p=0.xx)”. Eight panels will be created with 4 rows to represent the four 2018/2019 QIV strains and 2 columns to represent Day 1 and Day 29.]

[figure not shown]

Figure with Similar format:

Figure 91: Association of Non-neutralizing Fc-effector Antibody Titers and Neutralizing Antibody Titers against 2018/2019 QIV Strains by Study Day and Study Arm, Per Protocol Population

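### At Day 29, SAP Figures 90 and 91 print only a Spearman r and p pooled over six randomised arms, so arm differences in both assays can pass for an association between subjects

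*SAP*

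**What the plan says.** Protocol Table 1 lists an exploratory objective: "To evaluate the relationship of non-neutralizing Fc-effector antibodies titers with HAI and NA responses" after the 2018/2019 vaccines with and without adjuvant. The paired outcome measure names HAI and Neut, and the SAP figures follow it.

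SAP section 8.3 refers the analysis to figures in Appendix 2. The implementation notes for Figure 90 (HAI) and Figure 91 (Neut) give the same rule: "The spearman correlation should be calculated over all subjects and annotated within each panel as" "Spearman Correlation (r=0.xx, p=0.xx". Panels are laid out as four strain rows and "2 columns to represent Day 1 and Day 29". They are not split by arm. Study arms are marked by colour, symbol and, in Figure 90, fill. Both titles promise a display by study day and study arm, but the one statistic in each panel ignores arm. We found no within-arm, stratified or partial correlation specified for this association in either document.

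**The concern.** Subjects are "randomly assigned with allocation (1:1:1:1:1:1) to one of 6 study arms". Protocol section 11.1 explains why: "These study arms are included to allow evaluation of the potential of each of the two adjuvants to enhance the immune response to either" of the two vaccines. HA content also differs by vaccine (60 µg for Fluzone, 180 µg for Flublok; Protocol section 6.1.1). Differences between arms in mean Day 29 titer are therefore plausible.

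If such differences occur in both assays, high-responding arms sit at the upper right of the scatter and low-responding arms at the lower left. A pooled rank correlation then turns positive even if, inside every arm, a subject's HAI or Neut titer says nothing about that subject's Fc-effector titer. Opposite shifts would give a spurious negative value. A reader who sees r and p is likely to conclude that the two antibody functions go together from subject to subject. Eight Day 29 correlations are exposed, and several could look significant together for this one reason.

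**Working it through.** The plan states no expected r, power or error rate for this correlation, so there is no figure of its own to reproduce.

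**Inputs**
- Six arms with equal allocation (SAP section 4.4.3).
- 38 evaluable subjects per arm: "it is expected that at least 38 subjects per group will be available for the primary immunogenicity analysis" (Protocol section 11.4.2). Pooled N = 6 × 38 = 228.
- Significance level 0.05, unadjusted (SAP section 5); two-sided is assumed.
- Assumed, because the documents give no values: the arm shifts in units of the within-arm SD, normal log titers, and Fc-effector results for all 228 subjects. The true within-arm correlation is set to 0.

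**Approximate pooled r.** Let a fraction f of subjects be shifted by d SD in both assays. The between-arm variance, and equally the between-arm covariance, is f(1−f)d². With no within-arm covariance and unit within-arm variance, the pooled product-moment correlation is about

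r = f(1−f)d² / [1 + f(1−f)d²].

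For the AF03 arms, f = 2/6 and f(1−f) = 0.222.
- d = 0.5: 0.0556 / 1.0556 = 0.053.
- d = 1: 0.222 / 1.222 = 0.182.

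**Threshold.** With 226 degrees of freedom and t = 1.97, p<0.05 requires |r| above 1.97 / √(226 + 1.97²) = 0.130. A pooled r centred on 0.18 exceeds that in most trials.

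**Simulation.** 2,000 to 4,000 replicates per scenario, independent normals within each arm, pooled Spearman:

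| Shift (SD) | Mean pooled r | Pooled p<0.05 |
|---|---|---|
| None (as at Day 1) | 0.00 | 5% |
| Four adjuvanted arms, both assays, 0.25 | 0.01 | 6% |
| AF03 arms, both assays, 0.5 | 0.05 | 12% |
| Four adjuvanted arms, both assays, 0.75 | 0.11 | 39% |
| AF03 1 and Advax-CpG55.2 0.5, both assays | 0.14 | 57% |
| AF03 arms, both assays, 1 | 0.18 | 78% |
| Flublok arms, both assays, 1 | 0.20 | 87% |
| Four adjuvanted arms, opposite directions, 1 | −0.18 | 79% |
| Four adjuvanted arms, HAI only, 1 | 0.00 | 4% |

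The simulated means agree with the formula.

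**Same type of data, arm-adjusted.** Rank each variable over all subjects, subtract the arm mean rank, correlate the residuals, and test on 228 − 2 − 5 = 221 degrees of freedom. Across the no-shift, AF03, AF03-plus-Advax and HAI-only scenarios the mean r is about 0, and p<0.05 occurs in about 5% of trials.

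**The case against.** The pooled Spearman is a legitimate description of the marginal association across all vaccinees. The objective spans every vaccine and adjuvant condition, and the outcome measure is worded in GMTs and rates, which are group-level quantities. A reader might infer that the objective demands a within-arm correlation. It does not say so, and the pooled r is not wrong as a description. What stands against it is that it is the only statistic in the panel, carries a p-value, and cannot separate the two sources.

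A reader might also infer that the documents establish that adjuvants raise both assays. They do not. They speak of potential to enhance the response, report higher HAI and neutralizing titers for related adjuvanted vaccines, and give no effect size for Fc-effector titers. Without a shift in both assays there is no inflation.

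The analysis is exploratory, SAP section 8.3 plans no formal hypothesis testing, arm clustering is visible through the plotting symbols, and listings give subject-level titers by arm. Even at 1 SD the spurious r is weak, about 0.18. All of this lowers the stakes. It does not correct a p-value printed in the panel.

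Finally, six within-arm p-values for each Day 29 panel would mean 6 × 8 = 48 further tests at about 38 subjects each, inviting chance findings. That objection is accepted, and the fix avoids it.

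**Conclusion.** The point holds for the eight Day 29 correlations in Figures 90 and 91, and is conditional on arm means differing in both assays. Under the stated assumptions, the chance of a significant pooled p with no within-arm association is about 12% when the AF03 arms shift by 0.5 SD, and 78% at 1 SD. It is close to nominal at 0.25 SD or when only one assay shifts. Day 1 is unaffected because randomised arms then differ only by chance.

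The shift sizes are assumptions, so the figures show what could happen and do not predict this trial's result. Nor do they show that any observed association would be spurious: a real within-arm association may exist, and pooling could inflate, mask or reverse it. Because the analysis is exploratory and no decision rests on it, this is a worthwhile, low-cost improvement and not a threat to the trial's main conclusions.

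**What to change.** In the implementation notes for Figures 90 and 91, replace the Day 29 annotation with an arm-adjusted (partial) Spearman r and p: rank over all subjects, centre the ranks within study arm, and reduce the degrees of freedom by five for the six arms. Keep the pooled r beside it if wanted, labelled as unadjusted and descriptive, without a p-value. Within-arm r values are optional and should be shown without p-values. The Day 1 annotation can stay as it is.

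The cost is a few lines of SAP text and code. No new data, assays or visits are needed.

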14.3.1.1 Solicited Adverse Events

Figure 96: Maximum Severity of Solicited Systemic Symptoms per Subject by Day Post First Vaccination

[Implementation Note: A Generic figure is shown below. A vertical bar chart should be presented in 1 image file with separate panels for each study arm (6 panels: Top row: Groups 1, 2, 3; Bottom row: Groups 4, 5, 6). Axes should be labeled as follows: x-axis label: Study Day, y-axis label: Percentage of Subjects (%). The study arms should be indicated in the panel headers including “(N=X)”, where N = the number of subjects in the in the Safety Population who received the first study vaccination. Subjects are counted at most once at the maximum severity across all systemic events reported for the specified time point]

[figure not shown]

Figure with similar format:

Figure 97: Maximum Severity of Solicited Local Symptoms per Subject by Day Post First Vaccination

14.3.1.2 Unsolicited Adverse Events

Figure 98: Frequency of Unsolicited Adverse Events by MedDRA System Organ Class and Severity

[Implementation Note: A Generic figure is shown below. This figure includes all unsolicited events across all doses. A horizontal bar chart should be presented in 1 image file separate panels for each study arm (6 panels: Top row: Groups 1, 2, 3; Bottom row: Groups 4, 5, 6). Axes should be labeled as follows: y-axis label: System Organ Class, y-axis label: Number of Events. The study arms should be indicated in the panel headers including “(N=X)”, where N = the number of subjects in the in the Safety Population. The y-axis should present all SOCs reported by at least 1 subject and an “All Events” category. Y-axis should be sorted with “All Events first, then in decreasing order of total incidence]

[figure not shown]

Figure 99: Incidence of Unsolicited Adverse Events by MedDRA System Organ Class and Maximum Severity

[Implementation Note: A Generic figure is shown below. This figure includes all unsolicited events across all doses. A horizontal bar chart should be presented in 1 image file with separate panels for each study arm (6 panels: Top row: Groups 1, 2, 3; Bottom row: Groups 4, 5, 6). Axes should be labeled as follows: y-axis label: System Organ Class, x-axis label: Percentage of Subjects (%). The study arms should be indicated in the panel headers including “(N=X)”, where N = the number of subjects in the in the Safety Population. Subjects are counted at most once at the maximum severity across for any events in the applicable SOC. The y-axis should present all SOCs reported by at least 1 subject and an “All Events” category. Y-axis should be sorted with “All Events” first then in decreasing order of total incidence]

[figure not shown]

Figure 100: Frequency of Adverse Events by MedDRA System Organ Class and Relationship to Treatment

[Implementation Note: A generic sample figure is shown below. This figure includes all unsolicited events across all doses. A horizontal bar chart should be presented in 1 image file with separate panels for each study arm (6 panels: Top row: Groups 1, 2, 3; Bottom row: Groups 4, 5, 6). Axes should be labeled as follows: y-axis label: System Organ Class, y-axis label: Number of Events. The study arms should be indicated in the panel headers including “(N=X)”, where N = the number of subjects in the in the Safety Population. The y-axis should present all SOCs reported by at least 1 subject and an “All Events” category. Y-axis should be sorted with “All Events” first then in decreasing order of total frequency]

[figure not shown]
[figure not shown]

Figure 101: Incidence of Adverse Events by MedDRA System Organ Class and Relationship to Treatment

[figure not shown]
[Implementation Note: A Generic figure is shown below. This figure includes all unsolicited events across all doses. A horizontal bar chart should be presented in a 1 image file with separate panels for each study arm (6 panels: Top row: Groups 1, 2, 3; Bottom row: Groups 4, 5, 6). Axes should be labeled as follows: y-axis label: System Organ Class, x-axis label: Percentage of Subjects (%). The study arms should be indicated in the panel headers including “(N=X)”, where N = the number of subjects in the in the Safety Population. Subjects are counted at most once at the maximum relationship (related >not-related) across for any events in the applicable SOC. The y-axis should present all SOCs reported by at least 1 subject and an “All Events” category. Y-axis should be sorted with “All Events first, then in decreasing order of total incidence across groups]

14.3.5 Displays of Laboratory Results

Figure 102: Laboratory Results at Day 8: Mean Changes from Baseline by Laboratory Parameter and Study Arm – White Blood Cells

[Implementation note: A generic figure is shown below. Plot should be generated with all study arms in a single image file single panel with six boxplots to represent six study arms. Y-axis should be labeled “[Parameter] Change from baseline ([units]) and x-axis will be labeled ‘Study Arm’. Repeat for all clinical laboratory parameters: WBC, Hgb, PLT, ALT, AST, T. Bili, GGT, ALP, AMY, LIP, Cr]

Figures with similar format:

- Figure 103: Laboratory Results at Day 8: Mean Changes from Baseline by Laboratory Parameter and Study Arm – Hemoglobin**
- Figure 104: Laboratory Results at Day 8: Mean Changes from Baseline by Laboratory Parameter and Study Arm – Platelets**
- Figure 105: Laboratory Results at Day 8: Mean Changes from Baseline by Laboratory Parameter and Study Arm – Alanine Aminotransferase (ALT)**
- Figure 106: Laboratory Results at Day 8: Mean Changes from Baseline by Laboratory Parameter and Study Arm – Aspartate Amino Transferase (AST)**
- Figure 107: Laboratory Results at Day 8: Mean Changes from Baseline by Laboratory Parameter and Study Arm – Total Bilirubin**
- Figure 108: Laboratory Results at Day 8: Mean Changes from Baseline by Laboratory Parameter and Study Arm – Gamma-Glutamyl Transferase (GGT)**
- Figure 109: Laboratory Results at Day 8: Mean Changes from Baseline by Laboratory Parameter and Study Arm – Alkaline Phosphatase (ALP)**
- Figure 110: Laboratory Results at Day 8: Mean Changes from Baseline by Laboratory Parameter and Study Arm – Serum Amylase**
- Figure 111: Laboratory Results at Day 8: Mean Changes from Baseline by Laboratory Parameter and Study Arm – Serum Lipase**
- Figure 112: Laboratory Results at Day 8: Mean Changes from Baseline by Laboratory Parameter and Study Arm – Creatinine**

Listing 1: 16.1.6: Listing of Subjects Receiving Investigational Product

Subject ID	Randomized Study Arm	Product Received Study Vaccination 1	Product Received Study Vaccination 2

16.2 Database Listings by Subject**16.2.1 Discontinued Subjects****Listing 2: 16.2.1: Early Terminations or Discontinued Subjects**

Study Arm	Subject ID	Category	Reason for Early Termination or Treatment Discontinuation	Study Day

16.2.2 Protocol Deviations

Listing 3: 16.2.2.1: Subject-Specific Protocol Deviations

Study Arm	Subject ID	DV Number	Deviation	Deviation Category	Study Day	Reason for Deviation	Deviation Resulted in AE?	Deviation Resulted in Subject Termination?	Deviation Affected Product Stability?	Deviation Resolution	Comments

Listing 4: 16.2.2.2: Non-Subject-Specific Protocol Deviations

Site	Start Date	Deviation	End Date	Reason for Deviation	Deviation Resulted in Subject Termination?	Deviation Affected Product Stability?	Deviation Category	Deviation Resolution	Comments

16.2.3 Subjects Excluded from the Analysis

Listing 5: 16.2.3: Subjects Excluded from Analysis Populations

Study Arm	Subject ID	Analyses in which Subject is Included	Analyses from which Subject is Excluded	Results Available?	Reason Subject Excluded
		[e.g., Safety, ITT, PP]	[e.g., Safety, ITT, PP, Day x]		

Note: “Yes” in the “Results available” column indicates that available data were removed from the analysis. “No” indicates that no data were available for inclusion in the analysis.

